Study Design	A prospective, multi-center, randomized (1:1) clinical study evaluating the FLEX Vessel Prep device plus PTA (study arm) vs PTA alone (control arm) for the treatment of obstructive lesions in the native arteriovenous dialysis fistulae.
Sample Size	Up to 75 Subjects
Number of Sites	Up to 7 clinical sites in the United States.
Study Population	Subjects with a de novo or non-stented restenotic obstructive lesion up to 100 mm in length, located in the native arteriovenous dialysis fistulae in an upper extremity.

Inclusion Criteria	
 1. Patient is ≥ 21 years of age. 2. Patient has a life expectancy of ≥ 12 months. 3. Patient has a native AV fistula created ≥ 60 days prior to the index procedure. 4. The target AV fistula has undergone successful dialysis for at least 8 of 12 sessions during a four-week period. 5. Patient has a de novo and/or non-stented restenotic lesion located between approximately 2 cm proximal to the arteriovenous anastomosis and axillosubclavian junction with $\geq 50\%$ stenosis. 
Note: If the lesion is located in the cephalic arch, the treatment may be delivered up to 2 cm into the subclavian vein.
 
 6. Patient has a target lesion (which may include a tandem lesion) that is ≤ 100 mm in length (by visual estimate). 
Note: Tandem lesions may be enrolled provided they meet all the following criteria:
 
 • Separated from target lesion by a gap of ≤ 30 mm (3 cm). • Total combined lesion length, including 30 mm gap, ≤ 100 mm. • Able to be treated as a single lesion. 
 7. Patient has a target vessel diameter of 4mm – 12mm (by visual assessment). 8. Patient underwent successful crossing of the lesion with the guidewire. 9. Patient provides written informed consent prior to enrollment in the study. 10. Patient is willing to comply with all follow-up evaluations at specified times.

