Exclusion Criteria	
 1. Patient is pregnant or breastfeeding. 2. Patient is receiving immunosuppressive therapy. 3. Patient has undergone prior intervention of access site within 30 days of index procedure. 4. Patient with anticipated conversion to peritoneal dialysis. 5. Patient has an infected AV access or systemic infection. 6. Patient has planned surgical revision of access site. 7. Patient with secondary non-target lesion requiring treatment within 30-days post index procedure. 8. Patient with hemodynamically significant central venous stenoses that cannot be successfully treated prior to treatment of the target lesion. 9. Patient with target AVF or access circuit which previously had thrombectomy within last 30 days. 10. Patients judged to have a lesion that prevents complete inflation of an

	
angioplasty balloon or proper placement of the delivery system.
 
 11. Patient with target lesion located central to the axillosubclavian junction. 12. Patient has significant arterial inflow lesion requiring treatment more than 2 cm upstream from the anastomosis in the AV access. 13. Patient has presence of pseudoaneurysm or aneurysm requiring surgical revision at the target lesion site. 14. Patient with known contraindication, including allergic reaction, or sensitivity to contrast material that cannot be adequately pre-treated. 15. Patient who cannot receive recommended antiplatelet and/or anticoagulant therapy. 16. Patient with clinically significant Steal Syndrome requiring treatment. 17. Patient is enrolled in another investigational drug, device, or biologic study and has not completed the primary endpoint or was previously enrolled in this study. 18. Patient has a co-morbid condition that, in the judgment of the Investigator, may cause him/her to be non-compliant with the protocol or confound the data interpretation. 19. Patient has AV fistula created via endovascular technique.
Subject Follow-up	Subjects enrolled in the study will be followed up to 6 months. Follow-up assessments are scheduled for 30-days, 3- & 6-months post index procedure.
Time Course	
Start of enrollment: June 2021.
 
Completed enrollment: April 2022.
 
Planned study close-out: approximately October 2022.

4 Background

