This is a prospective, multi- center, randomized (1:1) clinical study evaluating the FLEX Vessel Prep System followed with PTA (TEST arm) vs PTA alone (CONTROL arm) for the treatment of *de novo* or non-stented restenotic obstructive lesions up to 100 mm in length located in the arteriovenous dialysis fistulae in an upper extremity. Enrollment will continue until complete data sets are collected for up to 75 subjects from up to 7 sites in the US.

Once enrolled, subjects will remain in the study through completion of the required follow-up duration unless the subject withdraws consent, the subject expires, the investigator withdraws the subject, or VentureMed terminates the study for any reason. The enrollment phase is expected to take 3 months. The follow-up duration for each subject is up to 6 months. The total expected duration of the study is approximately 9 months.

7 Product Description

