10.2 Potential Benefits

There are no guaranteed benefits from participation in the study. It is possible that treatment with the FLEX Vessel Prep System prior to use of PTA may improve and maintain blood flow through the treated AVF, resulting in the need for fewer treatments. This may allow for continued/resumption of AV access for the purpose of hemodialysis. Additionally, it is possible that lower balloon inflation pressures following FLEX Vessel Prep use will result in fewer complications and potentially less pain experienced during the procedure. Information gained from the conduct of this study may be of benefit to other persons with the same medical condition.

11 Serious Adverse Event Assessments

The Investigator is required to assess and document in the medical record all Serious Adverse Events (SAEs) observed in subjects from the time of enrollment until the event resolves or the subject exits the study. In cases in which SAEs are unresolved at the time of study exit, this will be documented on the CRF.

The Investigator is responsible for reporting SAEs to VentureMed as soon as possible, but no later than 10 working days after the Principal Investigator is first aware of the event, by completing the Adverse Event CRF. The Principal Investigator is responsible for reporting the SAE to the IRB as applicable.

12 Statistical Design and Methods

This is a prospective, multicenter, randomized (1:1) study of FLEX Vessel Prep prior to PTA vs PTA alone for the treatment of de novo and non-stented restenotic lesions in the AVF. The study will enroll at up to seven centers in the US.

Comparison of binomial proportions will be performed using Fisher's exact test. Time-to-event analyses using the Kaplan-Meier method may be conducted to supplement the primary analysis of proportions. Comparisons of continuous variables will be performed using a two-sample t-test or Wilcoxon rank-sum test.

For the primary efficacy endpoint and other 6-month endpoints that compare the proportion of subjects between arms, the numerator is the number of subjects with an event within 6 months and the denominator is the number of subjects with an event or who were followed for at least 150 days.

For the primary safety endpoint and other 30-day endpoints that compare the proportion of subjects between arms, the numerator is the number of subjects with an event within 30 days and the denominator is the number of subjects with an event or who were followed for at least 23 days.

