
The primary analysis will be based on intent-to-treat, including all subjects with available follow-up data analyzed by the arm to which they were randomized. Two-sided p-values less than 5% and one-sided p-values less than 2.5% will be considered statistically significant. For this post-market study, statistically significant differences are not anticipated. The study is intended to provide estimates of the differences between groups. Estimated differences and their 95% confidence intervals will be reported for all endpoints. For the primary efficacy endpoint, if primary patency rates are 60% and 80% in the control and treatment arms respectively, the 95% confidence interval width will be approximately $\pm 25\%$. For the primary safety endpoint, if SAE rates are 5% in both arms, the 95% confidence interval width will be approximately $\pm 17\%$.

Further details on the statistical methods, including justification, timing of interim analysis can be found in the Statistical Analysis Plan.

13 Ethics

The study will be conducted according to the study protocol, Clinical Trial Agreement, and all federal,

regulations, standards, and requirements including: 21 CFR Parts 11, 50, 54, 56, and 45 CFR part 46.

The clinical site will not begin enrolling subjects until the required approval/favorable opinion from the IRB has been obtained.

The site must provide VentureMed with a copy of the investigational site's IRB approval letter and the IRB-approved Informed Consent Form. If applicable, approvals for the continuation of the study must be kept current in accordance with the IRB's review schedule. All site communications to and from the IRB must be forwarded to VentureMed as they are sent/received.

VentureMed will be informed by the IRB and/or the Investigator in case any action is taken by an IRB with respect to this investigation.

This study was publicly registered on www.clinicaltrials.gov prior to first enrollment in accordance with the 2007 Food and Drug Administration Amendments Act (FDAAA).

14 Study Administration

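### The stated 95% CI half-widths (±25% efficacy, ±17% safety) have no stated n or interval method, and no method tried gives this pair at 75 subjects

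*Combined protocol and SAP*

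**What the plan says.** Section 12 (Statistical Design and Methods) says that significant differences are not expected and that the purpose is to estimate between-arm differences. It commits to intervals throughout: "Estimated differences and their 95% confidence intervals will be reported for all endpoints". It then gives the expected precision for the two primary endpoints:

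- Efficacy: "if primary patency rates are 60% and 80% in the control and treatment arms respectively, the 95% confidence interval width will be approximately" ±25%.
- Safety: "if SAE rates are 5% in both arms, the 95% confidence interval width will be approximately" ±17%.

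Neither sentence gives a number per arm or an interval method. The only method named for comparing proportions is Fisher's exact test, which does not by itself define an interval for a difference. Section 12 refers to a Statistical Analysis Plan for further detail, including justification, but no such text is in the document supplied.

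On size, the Protocol Summary says "Up to 75 Subjects" and Section 6 says "Enrollment will continue until complete data sets are collected for up to 75 subjects from up to 7 sites in the US". Allocation is 1:1 (Section 9.5). Section 12 restricts the denominators. For 6-month endpoints they count subjects with an event or at least 150 days of follow-up. For 30-day endpoints "the denominator is the number of subjects with an event or who were followed for at least 23 days". No loss rate is given. The Time Course row of the summary reads "Completed enrollment: April 2022".

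**The concern.** In a study with no power claim, margin or success criterion, the expected half-width is what tells a reader what the trial can show. A reader who takes the planned 75 subjects and the stated rates should be able to recover the two figures, at least to within a point or so. With the usual methods both come out smaller, and the safety figure by more than rounding can explain.

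The missing method also matters in its own right. At a 5% event rate with fewer than 40 per arm, the safety half-width ranges from about 10 to 22 points across the methods tabulated below. Section 12 promises intervals for every endpoint, so leaving the method open allows it to be chosen after the data are seen.

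**Working it through.** **Inputs.** Two-sided 95%, z = 1.96. Efficacy 0.80 (treatment) v 0.60 (control); safety 0.05 v 0.05 (Section 12). n = 38 and 37, the largest 1:1 split of 75 (Protocol Summary, Sections 6 and 9.5). Half-width = (upper − lower)/2.

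**Step 1: try to reproduce the plan's figures at 38/37.**

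Wald, z × √[p₁(1−p₁)/n₁ + p₂(1−p₂)/n₂]:

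- Efficacy: 1.96 × √(0.16/38 + 0.24/37) = 0.203
- Safety: 1.96 × √(0.0475/38 + 0.0475/37) = 0.099

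The Wald continuity correction adds ½(1/38 + 1/37) = 0.027, giving 0.229 and 0.125 from the unrounded values.

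Newcombe combines the single-arm Wilson limits by square-and-add:

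- Efficacy: Wilson limits (0.648, 0.897) for 0.80 and (0.440, 0.741) for 0.60.
  - Lower = 0.20 − √[(0.80−0.648)² + (0.741−0.60)²] = −0.007
  - Upper = 0.20 + √[(0.897−0.80)² + (0.60−0.440)²] = 0.387
  - Half-width 0.197
- Safety: Wilson limits (0.013, 0.169) for 38 and (0.013, 0.171) for 37 give (−0.127, 0.125), half-width 0.126.

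Miettinen-Nurminen inverts the score test, with variance at the restricted maximum-likelihood estimates times N/(N−1). It gives (−0.009, 0.396) for efficacy and (−0.130, 0.128) for safety.

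| Method at 38/37 | Efficacy (stated 25) | Safety (stated 17) |
|---|---|---|
| Wald | 20.3 | 9.9 |
| Wald, continuity-corrected | 22.9 | 12.5 |
| Agresti-Caffo | 20.0 | 11.5 |
| Newcombe | 19.7 | 12.6 |
| Newcombe, continuity-corrected | 21.4 | 14.5 |
| Miettinen-Nurminen | 20.2 | 12.9 |
| Exact unconditional, score statistic | 20.7 | 13.4 |
| Exact unconditional, raw difference | 21.9 | 22.3 |
| Clopper-Pearson limits, square-and-add | 21.6 | 13.3 |
| Clopper-Pearson limits, plain sum | 30.2 | 16.9 |

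The two exact unconditional rows use whole counts: 30/38 v 22/37 for efficacy and 2/38 v 2/37 for safety. The plain sum meets the safety figure but misses efficacy by 5 points. No row gives 25 with 17.

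**Step 2: find the n per arm that would give the stated pair.** For Wald, n = z² × [p₁(1−p₁) + p₂(1−p₂)] / h²:

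- Efficacy: 3.8416 × 0.40 / 0.25² = 24.6
- Safety: 3.8416 × 0.095 / 0.17² = 12.6

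The two n differ by a factor of two, so Wald cannot be the source at any single n. The same solution for the other methods:

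| Method | n per arm for ±25 | n per arm for ±17 |
|---|---|---|
| Wald, continuity-corrected | 32.1 | 22.9 |
| Agresti-Caffo | 23.5 | 20.0 |
| Newcombe | 22.4 | 23.8 |
| Miettinen-Nurminen | 24.4 | 24.9 |
| Newcombe, continuity-corrected | 27.6 | 29.8 |

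Only the last three give nearly one n for both figures. For example, Miettinen-Nurminen at 25 per arm gives 24.7 / 16.9. Newcombe with continuity correction gives 24.8 / 17.7 at 28 per arm and 24.0 / 16.9 at 30. The exact raw-difference interval gives 25.0 / 25.5 at 32 per arm and so does not fit the pair.

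**Step 3: test attrition as the explanation.** With an assumed 10% loss (34 per arm), Miettinen-Nurminen gives 21.2 / 13.7, still short. By the three methods that fit, the safety figure needs 24 to 30 evaluable per arm, or 48 to 60 of 75. That means 1 − 60/75 = 20% to 1 − 48/75 = 36% not evaluable under a rule that asks only for an event or 23 days of follow-up.

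**The case against.** The strongest reply is that no arithmetic error has been shown, only an undisclosed basis. The figures are called approximate and are not tied to 75 evaluable subjects, and 75 is a ceiling. The denominators exclude subjects with short follow-up, and Section 9.7 withdraws those whose access is abandoned. One method at one n does reproduce the pair. If ± is read as the longer side of an asymmetric interval, Newcombe with continuity correction at 30 per arm gives 25.4 / 16.9, which a cautious 20% allowance would explain. The Statistical Analysis Plan may hold the basis.

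Part of this stands. The n behind the figures is unknown, the pair is not impossible in itself, and the separate plan could settle it. The direction also depends on the method: the exact raw-difference safety interval is wider than stated.

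The mismatch remains. No loss rate is given, Section 6 counts complete data sets toward the 75, and even the favourable reading needs a fifth of subjects not evaluable at day 23. If a smaller planning number was used, Section 12 should give it beside the figures.

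It is also fair to say that the consequence is limited. The reported intervals will come from the data, and by the common methods the text undersells the study.

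**Conclusion.** The concern holds. Section 12 gives neither an n per arm nor an interval method for its half-widths, and none of the methods tried returns ±25% with ±17% at 37/38. Under Miettinen-Nurminen the stated values are too wide by about 5 points for efficacy (25 v 20.2) and 4 for safety (17 v 12.9); under Wald the safety gap is about 7 points.

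This rests on 75 evaluable subjects as the best case, on ± meaning half the interval length, and on allowing about one point for the word approximately. Confidence is high for the mismatch with 75. The smaller n, about 22 to 30 per arm, is an inference. This should be fixed, but it touches no decision rule.

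**What to change.** In Section 12:

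1. Name the confidence-interval method for differences in proportions.
2. Give the evaluable n per arm behind each figure, separately for the 150-day and 23-day denominators, with any assumed loss.
3. Restate both half-widths to match. Under Miettinen-Nurminen they are about ±20% and ±13% at 37/38, or ±21% and ±14% at 34 per arm. Under another method, use its row in the first table. This is the sponsor's choice.

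Since the summary records enrollment as complete, the numbers actually randomized per arm can be used, labelled as such. If a smaller evaluable number was intended, state it and reconcile it with the complete-data-set wording in Section 6. If the Statistical Analysis Plan already holds the basis, cite its section.

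The cost is one sentence and two numbers. Trial conduct does not change. Naming the method does settle a detail of the analysis that Section 12 now leaves open.

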14.1 Investigator Responsibility / Performance

The Investigator is responsible to ensure that all work and services related to this study described herein, or incidental to those described herein, are conducted in accordance with the highest standards of medical and clinical research practice, the requirements of the IRB, the protocol, and the terms of the Clinical Trial Agreement, and all applicable regulations.

The Investigator must maintain a Delegation of Authority Log of appropriately qualified persons to whom the Investigator has delegated significant study related duties.

14.2 Monitoring

Monitoring and monitoring oversight will be provided by VentureMed (i.e., contractors and authorized designees).

VentureMed will be responsible for ensuring adequate monitoring, including site initiation and study closure, to ensure the protection of the safety and rights of subjects, as well as the quality and integrity of the data collected and submitted. Frequency of monitoring will be based upon enrollment, study duration, site compliance, and any suspected inconsistency in data that requires investigation. After each monitoring visit, the monitor will send the Principal Investigator a letter summarizing the monitoring visit. The Principal Investigator will be responsible for ensuring that follow-up actions needed to resolve issues are completed in an accurate and timely manner.

When source data verification is performed, the monitor must be granted direct access to original source documentation or certified copies of the original source must be provided. Direct access must also be permitted for individuals conducting audits, IRB review and regulatory inspections.

If electronic source documentation is used at the site, the site must provide to the monitor:

- Direct access to the electronic medical record (e.g., the monitor is given a guest password to directly access the system) or
- Direct access to the electronic medical record by reviewing alongside appropriate study staff (e.g., a research coordinator).

14.3 Data Management

The Investigator will prepare and maintain adequate and accurate source documents designed to record all observations and other pertinent data for each subject device.

Study personnel at the site will enter data from source documents corresponding to a subject's visit/follow-up into the protocol-specific paper in a timely manner. Subjects will not be identified by name in the study database or on any study documents to be collected by the VentureMed (or designee) but will be identified by a site number and subject number.

If a correction is made on a CRF, the study staff member will line through the incorrect data, write in the correct data, and initial and date the change.

The Investigator is responsible for all information collected on subjects enrolled in this study. All data collected during this study must be reviewed and verified for completeness and accuracy by the Investigator. A copy of the CRF will remain at the Investigator's site at the completion of the study.

It is recommended that all data is completed and sent to VentureMed within 10 business days of the completion of the protocol-specified assessments or sooner as requested by VentureMed.

14.4 Data Queries

During the review of source documents and CRFs at the monitoring visits, any discrepancies noted will be queried by VentureMed or its designee and must be resolved by the site staff and Investigator in a timely manner. In addition, VentureMed, or its designee, may also generate data queries during routine or remote review of the data. These queries will be sent to the site and must also be resolved in a timely manner.

14.5 Confidentiality

Subject confidentiality will be maintained throughout the clinical study in a way that ensures the information can always be tracked back to the source data. For this purpose, a unique subject identification code consisting of the unique Site Number and Subject Number will be assigned and used to allow identification of all data reported for each subject.

To maintain confidentiality, the subject's name should not be recorded on any study document other than the informed consent form. This scenario will be covered in the Patient Informed Consent Form. In the event a subject's name/PHI is included for any reason, it will be redacted as applicable. In the event of inability to redact the identification (e.g., digital

media), it will be handled in a confidential manner by the authorized personnel.

Study data may be made available to third parties, e.g., in the case of an audit performed by regulatory authorities, provided the data are treated confidentially and that the subject's privacy is guaranteed.

The identity of a subject will never be disclosed if study data are published.

The study sites must comply with applicable subject confidentiality provisions of the Health Insurance Portability and Accountability Act (HIPAA) issued by the U.S. Department of Health and Human Services (HHS). All sites should maintain subject privacy in accordance with federal regulations (45CFR Parts 160 and 164), local regulations, and institutional requirements.

14.6 Investigator reports

The Investigator is responsible for the preparation (review and signature) and submission to the sponsor of all case report forms, adverse events, deaths, and any deviations from the protocol. If any action is taken by an IRB with respect to this clinical study, copies of all pertinent documentation must be forwarded to VentureMed in a timely manner. Reports are subject to inspection and to the retention requirements as described above for Investigator records.

If any action is taken by an IRB with respect to this clinical study, copies of all pertinent documentation must be forwarded to VentureMed in a timely manner.

Table 2: Investigator Reports per VentureMed Requirements

Report	Submit to	Description/Constraints
Withdrawal of IRB approval (or lapse in IRB approval)	Sponsor	The Investigator must report a withdrawal of approval by the reviewing IRB of the Investigator's part of the investigation within 5 working days.
Study Deviations	Sponsor and IRB	Prior approval is required for changes in the plan or deviations. All deviations should be reported to VentureMed group and IRB (as required) in a timely manner.
Progress report	Sponsor and IRB	The Investigator must submit a progress report to the sponsor and IRB at regular intervals, but in no event less than yearly.
Failure to obtain informed consent prior to enrolling patients into the study	Sponsor and IRBs	If an Investigator enrolls a patient into the study without obtaining informed consent, the Investigator shall report such use within 5 working days after enrollment.

